6.3. Performance Endpoints

The following performance endpoints will be assessed during follow-up visits:

- Improvement in INTERMACS™ and/or NYHA functional class
- Freedom from worsening heart failure resulting in hospitalization, LVAD implantation, or death
- Explant for recovery of ventricular function or cardiac transplantation

Secondary endpoints assessed at 6 and 12 months post implant include:

- Improvement in LVEF
- Improvement in Quality of Life scores
- Improvement in 6MWT

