Implantation procedure	
The C-Pulse Cuff and the Sense Lead are implanted through a chest incision and without the use of cardiopulmonary bypass. Only a small pericardiotomy is required, limiting the potential for bleeding and for post-operative adhesions. The ascending aorta is isolated and its circumference measured. The circumferential length is noted on the pre-marked wrap. The Cuff is passed around the aorta such that the inflating aspect of the Cuff is positioned on the outside curvature. The Cuff is then checked to fit the aorta conformably and that the circumferential marks are appropriate prior to securing of the wrap with sutures. Pre-loaded interrupted 'mattress' sutures are placed through the tail of the Cuff at the appropriate circumferential marks with the Cuff 'open', and such that the inflation chamber of the Cuff is always visualized. The sutures are then tied down and the wrap checked to be conformal to the aorta. The excess wrap fabric is trimmed off. A bipolar ECG Sense Lead is placed on the heart, most preferably the left ventricular free wall. The gas line of the Cuff is trimmed to length and it and the ECG Sense Lead are attached to the intra-corporeal "Y- connector" end of the Percutaneous Lead. The Percutaneous Lead is then tunneled beneath the rectus sheath, the extra-corporeal end of the Lead having a Patient Connector permanently attached.
 
Alternatively, the lines may be tunneled to an intermediary incision for connection, particularly if a less invasive surgical technique (sternal-sparing) is used. The Percutaneous Lead is designed to be exchanged or removed if required, the latter eliminating the exit site. If removal occurs, the Cuff and Sense Lead can remain within the thorax with the gas line of the Cuff and the connector of the Sense Lead capped off and accessible with minimal surgery in the subcutaneous tissue of the abdominal area. If the Cuff is infected, it should be removed.

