Performance Endpoints	
The following performance endpoints will be assessed during follow-up visits:
 
• Improvement in INTERMACS™ and/or NYHA functional class• Freedom from worsening heart failure resulting in hospitalization, LVAD implantation, or death• Explant for recovery of ventricular function or cardiac transplantation 
Secondary endpoints assessed at 6 and 12 months post implant include:
 
• Improvement in LVEF• Improvement in Quality of Life scores• Improvement in 6MWT
Safety Endpoints	
The following primary safety endpoints will be assessed throughout each subject's participation in the investigation:
 
• All cause and device-related mortality• Aortic disruption• Exit Site infection• Internal PIL/Cuff infection• Thromboembolism• Device malfunction• All protocol-defined adverse events
Data collection	
The study will aim to collect patient data while supported with C-Pulse therapy (i.e. the subjects will be censored from analysis if the device is permanently "off" unless due to signs of recovery). Data will be captured at the following time points: Baseline, procedure, discharge assessment, clinical follow-up at 6 weeks, 6 months, 12 months, 18 months, 2 years and yearly thereafter. Data from any other additional time points may be collected and analyzed if available.
 
Data from baseline and up to 5 years of follow-up will be captured in an electronic database. Hemodynamic performance and functional testing will be determined according to procedures based on standard center practices. Any protocol-defined adverse events, including adverse device effects and outcomes will be reported by the Investigator.

Sponsor	
Sunshine Heart Inc. [name] [name] USA

Sponsor Contacts	
[name], Director of Clinical Studies [contact] Email [contact] [name], European Medical Director [contact] email: [contact]

ABBREVIATIONS

ACC	American College of Cardiology
AE	Adverse Event
AHA	American Heart Association
CABG	Coronary artery bypass grafting
CCS	Canadian Cardiovascular Society
CEC	Clinical Events Committee
CHF	Congestive Heart Failure
CI	Cardiac Index
CIP	Clinical Investigation Plan
CO	Cardiac output
CPB	Cardiopulmonary Bypass
CRF	Case Report Form
CRT	Cardiac Resynchronization Therapy
CTS	Cardiothoracic Surgeon
DMC	Data Monitoring Committee
EAB	Extra Aortic Balloon
EC	Ethics Committee

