Another infection observed during the C-Pulse® clinical study was a pneumo-mediastinum infection that resulted from a breach in the PIL due to a patient fall. The rate of this incident is low, observed at 5%.

The risks associated with this type of infection are high if not properly managed. Resolution of this type of infection is normally managed through use of antibiotics and removal of the C-Pulse® System. Device related infections should be continuously monitored and treated accordingly to mitigate this risk (this statement is included in the C-Pulse System IFU). In addition, the revised exit site guidelines include lead stabilization techniques that will minimize trauma from falls or pulling on the exit site.

4.2. **Clinical Risk/Benefit Assessment**

The C-Pulse® uses proven balloon counter-pulsation technology to increase left ventricular coronary artery blood flow and cardiac output and to reduce the workload on the heart. The C-Pulse® System is an earlier intervention than other mechanical circulatory support therapies, such as LVADs, meeting a clinical need for relief of symptoms in heart failure patients that are refractory to optimal medical therapy and CRT therapy.

The C-Pulse® System is designed to treat clinical symptoms associated with Class III and ambulatory Class IV heart failure (INTERMACS™ category 4-7). These symptoms normally include shortness of breath, dizziness, low blood pressure and fluid retention. Patients associated with Class III and ambulatory Class IV heart failure are typically unable to engage in normal activities, compromising their quality of life.

C-Pulse® system has demonstrated patient benefits during the clinical studies to date which include the following:

- Reduction in NYHA classification by at least 1 class.
- Improvement in Quality of Life as demonstrated by MLWHF and KCCQ.
- Improvement in Ejection Fraction.
- Positive trend in 6 Minute Hall Walk capacity.
- Reductions of symptoms and the ability to be discharged and remain at home with their heart failure.

Other benefits characterize the device concept:

- C-Pulse® is designed to be implanted without the need for cardiopulmonary bypass or extensive dissection
- Device does not come in contact with blood, thus an anticoagulant therapy is not required.
- The C-Pulse® is not life-sustaining and can be disconnected as needed for personal hygiene.
- C-Pulse may be permanently stopped for patients who experience sustained left ventricular recovery.

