8.3. Deaths and Explants

8.3.1. . Subject Deaths

In the event of subject death, every effort should be made to obtain a copy of the autopsy report and/or death summary. Information on the cause of death and its relationship to the device used in this clinical investigation will be determined by the principal investigator. Copies of an autopsy report, if available, and/or a death summary are to be sent to the Investigation Sponsor.

If a device is explanted during autopsy, the device should be returned to the Investigation Sponsor for analysis. Return kits for devices will be provided upon request by the clinical monitor.

8.3.2. . Device Explants

In the event a device component is explanted in the intra-operative or early post-operative period (i.e., while the patient is hospitalized at the investigational center), a copy of the procedure report must be provided to the Investigation Sponsor. Information on the cause of explant and its relationship to the device component will be determined by the principal investigator. Explanted device components during this period must be returned to the Investigation Sponsor for analysis. Return kits for devices will be provided upon request by the clinical monitor.

In the event a device component is explanted in the late post-operative period, every effort should be made to obtain a copy of the explant procedure report, as applicable. Information on the cause of explant and its relationship to the device component will be

determined by the principal investigator. Copies of an explant report, if available, are to be sent to the Investigation Sponsor. Explanted device components during this period should be returned to the Investigation Sponsor for analysis. Return kits for devices will be provided upon request by the clinical monitor.

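### Device loss for reasons other than recovery or transplantation is not itself a performance failure, and the censoring rule can remove the heart-failure events that follow it

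*Combined protocol and SAP*

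**What the plan says.** Section 6.3, repeated in the Synopsis, lists three performance endpoints: "Improvement in INTERMACS™ and/or NYHA functional class"; "Freedom from worsening heart failure resulting in hospitalization, LVAD implantation, or death"; and "Explant for recovery of ventricular function or cardiac transplantation". The secondary endpoints are LVEF, quality of life and 6MWT at 6 and 12 months. Explant appears only in the third performance endpoint, and only for recovery or transplantation. Whether that endpoint counts as success or failure is not stated.

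The Synopsis (Data collection) says that "the subjects will be censored from analysis if the device is permanently 'off' unless due to signs of recovery". Section 5.6 gives the same rule without the recovery exception. Both describe the aim as collecting data while the patient is on therapy.

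The documents foresee removal for unfavourable reasons. The Synopsis (Implantation procedure) says "If the Cuff is infected, it should be removed". Section 4.3 calls for cuff explant when a sternal infection reaches bone. Of the mediastinal infection it says "Resolution of this type of infection is normally managed through use of antibiotics and removal of the" system. Section 8.3.2 states: "Information on the cause of explant and its relationship to the device component will be determined by the principal investigator". No endpoint uses that information. Section 6.4 lists infection and device malfunction among the primary safety endpoints.

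**The concern.** Two features of the plan act together. No performance endpoint treats a non-recovery explant or permanent stop as a failure, and the censoring rule takes the patient out of the analysis at that moment. Under the Synopsis wording, patients who stop because they recovered stay in while those who stop for bad reasons leave.

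Patients who lose the device to infection, malfunction or lack of benefit are likely to have a different later risk of heart-failure hospitalization, LVAD or death from those who remain on it. If that risk is higher, censoring at the stop raises the reported freedom. Section 4.1 gives the study's purpose as monitoring safety and performance and confirming favourable premarket results. A performance figure limited to patients still on the device answers a narrower question than that.

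**Working it through.** **Text check.** Each way of losing the device, against the endpoints:

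| Reason for permanent loss | Failure in 6.3 in its own right? | After the stop | Seen elsewhere? |
|---|---|---|---|
| Infection | No | Censored | The infection, under safety |
| Malfunction | No | Censored | The malfunction, under safety, once the manufacturer confirms it (8.2.4) |
| Lack of benefit or patient choice, no event | No | Censored | Not necessarily |
| Recovery | Named in endpoint 3 if explanted | Kept (Synopsis) or censored (5.6) | – |
| Transplantation | Named in endpoint 3 | Censoring not separately addressed | – |

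The composite can be read with worsening heart failure qualifying all three items or hospitalization only. Device loss is outside it either way.

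**Arithmetic.** The plan has no figure to reproduce here: the available text gives no performance target and no device-loss rate. Section 6.6 supplies N = 50. The other inputs are assumptions:

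- S, freedom from the composite at a fixed time if nobody lost the device: 60%, 70%, 80%.
- L, probability of non-recovery device loss by the same time: 5% to 30%.
- Loss independent of the composite events, and a time-to-event estimate censored at loss. Section 6.5 names no method.

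Censoring at loss estimates S. Counting loss as failure gives S × (1 − L). The gap is S × L.

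| S (reported under censoring) | L = 5% | L = 10% | L = 20% | L = 30% |
|---|---|---|---|---|
| 60% | 57% | 54% | 48% | 42% |
| 70% | 66.5% | 63% | 56% | 49% |
| 80% | 76% | 72% | 64% | 56% |

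The gap runs from 0.60 × 0.05 = 3 points to 0.80 × 0.30 = 24 points. It separates two definitions of performance and is not a pure estimation bias. Freedom from the composite regardless of device status lies between the two values if event risk off the device is at least as high as on it. To that extent the censored figure is too favourable.

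**Functional class, as a proportion.** Suppose 10 of 50 patients are lost and 28 of the remaining 40 improve. Dropping the lost patients gives 28/40 = 70% (exact 95% CI 53.5% to 83.4%). Counting them as non-improved gives 28/50 = 56% (41.3% to 70.0%). With 5 lost and 31 improved, the figures are 31/45 = 68.9% and 31/50 = 62.0%.

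**The case against.** A reader might infer that a lost device never enters the performance result. The text does not support that. A heart-failure hospitalization, LVAD or death before the stop fails the composite. A patient who gives up the device after a visit showing no improvement in class has not met the first endpoint. Direct conversion to LVAD can count through the LVAD.

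A reader might also picture patients without a working device being carried as event-free for years. The censoring rule prevents that; the difficulty is that they leave the analysis.

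Safety reporting does part of the work. Internal infection and malfunction are primary safety endpoints, and section 6.5 promises tables of patients available for follow-up and actually followed. Neither gives loss of therapy by cause. Malfunction or lead removal need not mean loss of therapy, since the lead can be exchanged and the implanted parts are meant to be replaceable (section 2.3.6). The 5-year figure in that section is the cuff's minimum intended use period, not a target for time on therapy.

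The size is also open to challenge, and fairly. The 5% in section 4.3 for the mediastinal infection is an infection rate, not a removal rate. One case in 20 has an exact 95% interval of 0.1% to 24.9%. It does not support a predicted number of lost devices among 50. The contents list announces premarket results that are not in the text available to me, so I make no claim about them.

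Finally, this is a single-arm descriptive study with no success threshold, and section 6.5 relies on endpoint consistency with the US trial. That is a good reason not to redefine the composite. It does not justify leaving device loss unreported or censoring the events that follow it.

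**Conclusion.** The concern holds in a limited form. Non-recovery device loss is not itself a performance failure, and the censoring rule can remove subsequent hospitalizations, LVADs and deaths from the freedom endpoint. The censoring is probably informative and its likely direction is favourable to the device. That judgement assumes that patients who lose the device for bad reasons do worse afterwards, which the documents neither state nor rule out.

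Under assumed freedom of 60% to 80% and independent loss of 5% to 30%, the reported figure is 3 to 24 points above one that counts loss as failure. These values show scale and are not forecasts. No figure in the documents is contradicted. This is a design weakness that should be corrected. The difference between the Synopsis and section 5.6 on recovery is an internal inconsistency that must be reconciled whatever view is taken of the rest.

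**What to change.** 1. Reconcile the censoring statements in the Synopsis and section 5.6. State which analyses the rule governs and how recovery is handled.
2. Keep the composite as it is, for consistency with the US trial. Beside it in section 6.3 and the Synopsis, list *explant or permanent device-off for any reason other than recovery*. Report its cumulative incidence by cause (infection, malfunction, lack of benefit, patient choice), with death, LVAD and transplantation as competing events. State that a device removed at LVAD implantation or transplantation is classed under that competing event.
3. Add a sensitivity analysis that counts non-recovery device loss as failure in the freedom and functional-class endpoints.
4. Do not censor heart-failure hospitalization, LVAD or death at device-off where follow-up data exist.

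Adding device-off to the composite without changing the censoring text would make the same event both a failure and a censoring time.

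Cost: explant causes (section 8.3.2) and the device log (section 5.6, Table 3) are already planned. Section 8.3.2 covers explanted components only and, for late explants, asks for reports only if available. One e-CRF field is therefore needed for the reason for permanent device-off without explant, plus one table and one sensitivity analysis. The stated performance will become less favourable.

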Chronic HF is conventionally treated with drugs. However there are many circumstances where drug therapy is insufficient or where the heart has become refractory to drug therapy. Cardiac Resynchronization Therapy (CRT) is suitable for approximately 30% of moderate HF (New York Heart Association - NYHA Class III) patients, and has been shown to provide significant clinical improvement. However, as many as 30% of patients who have CRT implants do not have a satisfactory response ("non-responders"). Further, many patients initially have a good response but then develop more advanced symptoms.

Heart transplantation is an effective therapy for end stage NYHA Class IV patients. However, the number of donor hearts falls short of meeting the needs of patients and many patients are excluded because of age (the upper limit for transplant being approximately 65 years)

Left Ventricular Assist Devices (LVADs) have been shown to offer the potential for the treatment of end stage NYHA Class IV HF patients. However, because of the blood-contacting nature, these devices have high associated risks such as bleeding, stroke, infection and device failure. Furthermore patients spend time in hospital due to these associated complications.

There is growing evidence that the unloading actions of LVADs can facilitate significant recovery and reverse remodeling of the heart. However, LVADs tend to be implanted late in the clinical course of heart failure, due to the risk profile versus the expected benefits.

Earlier implant may improve the chance of recovery of the heart. Therefore, there is a need for lower risk, lower cost devices that allow for long-term implant in less sick patients. Such a device could provide for partial unloading of the heart such that the patient can be weaned and for the device to not necessarily be removed.

1.5. . C-PULSE SYSTEM Innovation

Sunshine Heart's C-Pulse® System is a new approach for patients with moderate to severe heart failure that can be used in combination with other heart failure therapies. The device is designed to assist the heart's function, not replace it and may be implanted using a minimally invasive approach. The objective of the C-Pulse® system is to provide an effective, low risk and low cost mechanical heart assist device for use in patients in NYHA Class III-IV ambulatory.

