2. IDENTIFICATION OF THE DEVICE

2.1. . C-Pulse System Description

The C-Pulse® System (C-Pulse or C-Pulse System) has been proposed as a non-blood contacting wearable heart assist device to perform long-term aortic counterpulsation in patients suffering moderate to severe heart failure. The device is designed:

- to be simple to implant,
- to accommodate aortic anatomic variability,
- to be safe for the aorta and have a high cycle-life,
- to provide measurable improvement in hemodynamic variables,
- to allow mobility,
- to be able to be turned off or used intermittently if left ventricular recovery occurs, and
- to be able to be disconnected.

Figure 1 below provides a graphic representation of the C-Pulse® System. The system provides cardiac assistance through an extra-aortic balloon Cuff and ECG sense lead connected by means of a Percutaneous Interface Lead (PIL) to an external pneumatic Driver. The PIL and external driveline are held securely externally with 2-3 simple adhesive clips for immobilization of the Driver lead and external part of the PIL at the exit site. The Driver is adjusted using a dedicated notebook computer (the Programmer) with specialized software. The Driver inflates and deflates the Cuff in counter-synchrony to the cardiac cycle. The C-Pulse® System has been designed to have simple, effective and safe implantable components (the Cuff and PIL) and an external wearable component (the Driver). The C-Pulse System sits outside the bloodstream, reducing the risk of stroke and blood clots and therefore eliminating the need for anti-clotting medications directly related to the C-Pulse System.

[figure not shown]

Figure 1. Sunshine Heart C-PULSE SYSTEM

2.2. . Intended Purpose and Indications

The C-Pulse® System is indicated for use in patients with moderate to severe heart failure [American College of Cardiology/American Heart Association (ACC/AHA) Stage C; NYHA Class III/IV ambulatory], who are refractory to optimal medical therapy. The C-Pulse® System is intended to relieve the symptoms of heart failure, improve quality of life and cardiac function.

[figure not shown]

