The C-Pulse provides the patient with a treatment option avoiding or delaying the need for VAD and/or transplant procedure. The average time on the C-Pulse® device for patients is 335 days (to date) and two patients were successfully weaned from C-Pulse® within one year. Therefore, treatment with the C-Pulse® may extend the time before a patient may require a VAD or transplant, if at all.

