Observed rate of exit site infections in the C-Pulse® clinical study was 40%. However the risks associated with this type of infection are low. Normally the resolution of this type of infection is managed through use of antibiotics, antiseptics, exit site management and PIL stabilization. Since C-Pulse® is not blood contacting, the risk of sequelae, particularly sepsis, is significantly less than observed with LVADs, thus exit site infections with the C-Pulse® device are not as high a risk as in LVADs. There remains a risk of ascending infection – exit-site pain, tenderness or swelling over the subcutaneous flocking, etc., should be investigated and treated aggressively. The PIL is specifically designed as a modular component of the C-Pulse® System, such that if an infection is chronic the PIL can be removed and the infection easily treated with antibiotics.

Adoption of the requirement for a stabilization device and new infection management techniques and protocol will require the sites to treat the C-Pulse® PIL as critically as the VAD drivelines to facilitate minimizing infection. The anticipated rate of residual risk in the post-market experience following implementation of the mitigations is expected to be no greater

than 30%. This rate is acceptable since it is consistent with what is currently being experienced with other devices having a drive-line exit site.

The clinical benefit of the PIL and its design features (e.g. ease of accessibility, ability for the patient to temporarily disconnect, removability) continue to support that the benefit outweighs the residual risk.

2) Sternal wound infection

During the C-Pulse® clinical study, one patient experienced a sternal wound infection resulting from the surgical procedure. The outcome of the management of the sternal wound after several attempts for debridement and a sternal flap was an aortic disruption. The rate of this incident is low, observed at 5% (1/20).

The risks associated with this type of infection are high if not properly managed. Resolution of this type of infection is normally managed through use of antibiotics and sternal wound debridement and drainage. If the sternal wound infection progresses to include the sternal bone the Cuff should be explanted to avoid infection of the Device.

3) Pneumo-mediastinum Infection

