- The device does not preclude future use of an LVAD or heart transplantation if required (bridge function).
- The C-Pulse® is provided with features that facilitate the management of adverse events.

C-Pulse® does not directly contact the patient's blood and it may be turned on or off at any time allowing the patient intervals of freedom to perform certain activities. Because the C-Pulse® remains outside the circulatory system, there is negligible risk of device-related bleeding, blood clots and stroke in comparison to other mechanical devices that reside or function in the bloodstream. The risk associated with device failure is also significantly less. C-Pulse® allows for weaning of the device if there is sustained cardiac recovery. Heart function replacement therapies such as LVAD or heart transplantation remain therapeutic options if heart failure progresses.

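### The only endpoint that names recovery counts explants, so a patient taken off C-Pulse support for recovery with nothing removed is not counted, and lead-only removal is ambiguous

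*Combined protocol and SAP*

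**What the plan says.** The performance endpoints in section 6.3, repeated in the synopsis, contain one line that names recovery: "Explant for recovery of ventricular function or cardiac transplantation". Neither place defines explant, and it is not among the event definitions in section 8.2.4.

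Several other sections describe recovery without requiring removal:

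- Section 1.4, on what a device of this kind could offer: "the patient can be weaned and for the device to not necessarily be removed".
- Section 2.1, among the design aims: "to be able to be turned off or used intermittently if left ventricular recovery occurs".
- Clinical Risk/Benefit Assessment: "C-Pulse may be permanently stopped for patients who experience sustained left ventricular recovery". Later in the same section, the device "allows for weaning of the device if there is sustained cardiac recovery".
- C-Pulse System Benefits, on premarket experience: "two patients were successfully weaned from C-Pulse® within one year".

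The plan also recognises partial removal. The synopsis entry on the implantation procedure says that after removal of the percutaneous interface lead (PIL) "the Cuff and Sense Lead can remain within the thorax". Table 2 in section 2.4 lists a gas-line cap for partial explants, and section 8.3.2 handles explants component by component.

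The two censoring statements differ. The synopsis (Data collection) censors patients whose device is permanently off, except where this is because of recovery. Section 5.6 has the same rule without the exception.

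**The concern.** The endpoint records a surgical act, whereas the plan describes recovery as a change in the need for support. A patient can meet the plan's own description of recovery and never meet the endpoint. Whether that happens depends on whether hardware is taken out, and practice on that may differ between up to 15 European sites.

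Two things are at stake. The reported recovery count may be too low. It may also vary between sites for reasons unrelated to ventricular function, because a PIL-only removal can be scored as an explant at one site and not at another. Section 4.1 says the study is meant to confirm the premarket results, and section 6.5 foresees pooling and comparison with the US trial, so what this line counts needs to be clear.

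**Working it through.** No figure in the plan depends on this endpoint, and the text of section 6.6 does not tie the sample size of 50 to it. There is therefore no stated figure to reproduce. The check is a comparison of the sections, followed by an illustration of size.

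**Step 1. Apply the endpoint to each way of recovering.**

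| Support stopped for recovery, and what was removed | Recovery event under section 6.3? |
|---|---|
| Cuff, sense lead and PIL | Yes |
| PIL only, cuff and sense lead capped and left | Unclear: explant is undefined, and sections 2.4 and 8.3.2 use it at component level |
| Nothing | No |

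The third row is the pathway that section 2.1 and the risk/benefit section describe without mentioning removal, and that section 1.4 says need not involve it.

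**Step 2. Is the patient in the third row still in the analysis?** Under the synopsis, yes, through the recovery exception. Under section 5.6, no: the device is permanently off, so the patient is censored. The synopsis thus treats device-off for recovery as a distinct state but provides no endpoint that counts it.

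**Step 3. Direction.** Recovery without explant can be missed, and nothing in the rule adds recoveries that did not occur. From this source the recovery count can only be too low.

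**Step 4. Size, as an illustration only.** Inputs:

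- 2 weaned patients (C-Pulse System Benefits).
- A denominator of 20, taken from the 1/20 given for other events in section 4.3. That it applies to the weaned patients is an assumption.
- 50 patients (section 6.6).
- The share s of recovered patients who have an explant, which no document gives.

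Calculations:

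- Premarket rate: 2/20 = 10%. The exact (Clopper-Pearson) 95% interval is 1.2% to 31.7%.
- Expected recoveries in 50 patients: 50 × 0.10 = 5. At the interval limits: 50 × 0.0123 = 0.6 and 50 × 0.317 = 15.8.
- Counted = 5 × s and missed = 5 × (1 − s). For s = 1, 0.5 and 0, the counts are 5, 2.5 and 0, with 0, 2.5 and 5 missed.
- At the extremes, the report would show 5/50 = 10% (exact 95% interval 3.3% to 21.8%) or 0/50 = 0% (0% to 7.1%) for the same patients.

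The premarket figure covers one year and this study follows patients for five, so applying the rate unchanged is a further assumption.

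**The case against.** The strongest reply is that explant is an objective, documented event, whereas stopping support for recovery is an investigator's judgement in an open-label study. Changing the endpoint might also disturb the consistency with the US trial on which section 6.5 relies, and the US definition is not in these documents. This has force. It is a reason to keep explant as a separately reported count, but not to leave the other recoveries uncounted.

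A second reply is that improvement in functional class, LVEF, quality of life and walk distance would register the benefit in these patients. In part it would. But all of these can improve while the patient is on support, so none identifies a patient who recovered and came off it. LVEF, quality of life and walk distance are endpoints only at 6 and 12 months.

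A reader might also infer more than the documents support:

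- *That recovered patients in general go uncounted.* Those explanted for recovery are counted.
- *That leaving the cuff in place means not being counted.* PIL removal with the cuff retained may qualify as a component explant. The plan does not say.
- *That the sections cited all describe cuff retention after recovery in this study.* Section 1.4 is background on a class of device, the synopsis statement on PIL removal does not mention recovery, and the risk/benefit section does not say what happens to the hardware.
- *That weaning is a main demonstrated benefit.* The risk/benefit section lists permanent stopping under the device concept, not among the demonstrated benefits.
- *That the endpoint cannot be compared with the premarket count.* The documents do not say whether the two weaned patients had anything removed, so this is unknown.

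**Conclusion.** The point holds in a limited form. A patient whose support is permanently stopped for sustained recovery with no component removed follows a pathway the plan describes, yet is not counted as a recovery. PIL-only removal is ambiguous. Under section 5.6, though not under the synopsis, such patients would also be censored.

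The direction of the error follows from the wording; its size does not. The range of 0 to 5 missed recoveries among 50 patients rests on three assumptions: a premarket denominator of 20, a one-year rate carried over unchanged, and an unknown share explanted. The 1.2% to 31.7% interval shows how weak the starting rate is. It should not be read as an estimate of bias.

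The study is observational, its final report is descriptive, and no test or threshold uses this line. The change is worth making because it is cheap and because the endpoint as worded can miss the outcome it names.

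**What to change.** In section 6.3 and the synopsis:

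1. Define the recovery component as permanent discontinuation of C-Pulse support for recovery of ventricular function, with or without removal of any component.
2. Report explant for recovery as a separate sub-category, and define explant, saying explicitly whether PIL-only removal qualifies. This keeps the objective event and any comparison with the US trial.
3. Record which components were removed (none, PIL only, cuff or sense lead) and any later restart of support.
4. Reconcile the censoring rule in section 5.6 with the recovery exception in the synopsis, so that these patients stay in the analysis.

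This sets what is counted. It does not address when support should be stopped. Intermittent use after recovery, which section 2.1 also mentions, would remain outside the count, and the definition should say so.

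The cost is a wording change in a few places and at most a small addition to the e-CRF, with no extra visits. The e-CRF itself is not in the documents, so part of this may already be captured. The downside is that discontinuation for recovery is an investigator's judgement in an open-label study and may be reversed, which is why explant is still shown separately and restarts are recorded.
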